To assess the efficacy of the escitalopram therapy under different dosing regimens we will use 21-item Hamilton rating scale for depression (HAM-D). Depression severity score will be measured at baseline (V0), at week 4 (V1) and week 8 (V2) after the beginning of the treatment. Since there is the need to compare depression severity scores between two test groups as well as between the visits V1 and V2, mixed analysis of covariance (Mixed ANCOVA) will be used if all assumptions associated with ANCOVA are met. Variables will be assigned as follows:

1. Dependent variable: Depression severity score measured by HAM-D scale
2. Independent variable - Fixed factor: Test group (Personalized vs Standard dosing)
3. Independent variable - Repeated measurements: Visit (Visit 1 vs Visit 2)
4. Covariates: Baseline HAM-D score (V0), Childhood trauma questionnaire score at V0, Age, Sex (Male=0, Female=1), Smoking status (0=Non-smoker, 1=Smoker), Alcohol consumption (0=No, 1=Yes), Metabolic syndrome diagnosed using siMS score [Soldatović 2016] (0=No, Yes)

Positive outcome: interaction between group and visit is significant ($\alpha=0.05$)

Besides using absolute HAM-D scores, we will also compare relative changes in HAM-D scores between V1 and V2 visits as another way to express the potential differences in therapy efficacy between the two test groups. If all needed assumptions are met, statistical test used will be analysis of covariance (ANCOVA) with variables assigned as follows:

1. Dependent variable: Relative change in HAM-D score between visits V1 and V2 calculated by formula:

$$\frac{HAMD_{V1} - HAMD_{V2}}{HAMD_{V1}}$$

2. Independent variable: Test group (Personalized dosing vs Standard dosing)
3. Covariables: Baseline HAM-D score (V0), Childhood trauma questionnaire score at V0, Age, Sex (Male=0, Female=1), Smoking status (0=Non-smoker, 1=Smoker), Alcohol consumption (0=No, 1=Yes), Metabolic syndrome (0=No, Yes)

Positive outcome: Test group is a significant factor ($\alpha=0.05$)

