Other primary outcome we will use to quantify changes in clinical outcomes between test groups will be severity of the treatment side effects measured using clinician reported UKU (*Udvalg for Kliniske Undersogelser*) side effect rating scale. UKU scale rates 48 potential adverse reactions with intensity score ranging from 0 to 3 where score 3 signifies maximal intensity and score 0 signifies absence of the adverse reaction. Adverse drug reaction intensity scores for all 48 adverse reactions monitored with UKU scale will be measured at weeks 4 (V1) and 8 (V2) after the initiation of the escitalopram therapy. Due to large number of comparisons, significance measures will be adjusted using False Discovery Rate (FDR) correction. Absolute values of all 48 Adverse reaction scores will be compared between test groups and between two time points using mixed model analysis of covariance (Mixed ANCOVA) where variables will be assigned as follows:

1. Dependent variable: Adverse drug reaction score for the given adverse reaction measured by UKU scale
2. Independent variable - Fixed factor: Test group (Personalized vs Standard dosing)
3. Independent variable - Repeated measurements: Visit (Visit 1 vs Visit 2)
4. Covariables: Age, Sex (Male=0, Female=1), Smoking status (0=Non-smoker, 1=Smoker), Alcohol consumption (0=No, 1=Yes), Coffee consumption (0=No, 1=Yes), Use of psychoactive substances (0=No, 1=Yes), Metabolic syndrome (0=No, 1=Yes), Creatinine clearance, AST/ALT ratio.

Positive outcome: interaction between group and visit is significant ($\alpha=0.05$)

Alternatively, proportions of patients with intensity score greater than 0 (UKU scale intensity score >0 signifies the presence of the given adverse reaction) will be compared between the groups for all 48 adverse effect monitored with UKU scale at two time points: 4 weeks after the enrolment (V1) and 8 weeks after the enrolment (V2). Due to large number of comparisons, significance measures will be adjusted using False Discovery Rate (FDR) correction. Proportion of individuals in two test groups affected with the given adverse reaction will be compared using binary logistic regression analysis separately for visit V1 and visit V2 as follows:

1. Dependent variable: Frequency of the individuals affected with the given adverse drug reaction measured by UKU scale

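### The primary HAM-D and UKU tests use a two-visit Mixed ANCOVA with no stated estimation method and no rule for patients without V2; run in its classical form, it is biased if V1-related dropout acts differently in the two groups.

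*Combined protocol and SAP*

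**What the plan says.** All references are to the Statistical Analysis Plan, Primary outcomes, unless stated.

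- **HAM-D, timing:** "Depression severity score will be measured at baseline (V0), at week 4 (V1) and week 8 (V2) after the beginning of the treatment".
- **HAM-D, main test:** "mixed analysis of covariance (Mixed ANCOVA) will be used if all assumptions associated with ANCOVA are met". Test group is the between-patient factor and Visit, with levels V1 and V2, is the repeated factor. The V0 score is a covariate. A significant group-by-visit interaction at 0.05 is the positive outcome.
- **HAM-D, second test:** an ANCOVA on "Dependent variable: Relative change in HAM-D score between visits V1 and V2 calculated by formula", which needs both visits unless values are imputed.
- **UKU, main test:** the 48 items are each analysed "using mixed model analysis of covariance (Mixed ANCOVA) where variables will be assigned as follows", again with Visit as repeated factor and the interaction as criterion. The covariate list has no baseline UKU score.
- **UKU, alternative test:** "binary logistic regression analysis separately for visit V1 and visit V2", which does not need pairs.

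The documents contain no analysis set, expected dropout, missing-data rule, estimation method, covariance structure or sensitivity analysis for incomplete follow-up.

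**The concern.** A between-within ANCOVA in its classical form needs a value at every level of the repeated factor, so a patient seen at V1 but not at V2 is dropped. With two visits, the interaction is then a comparison of V2−V1 change among completers.

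Change depends on the starting value through regression to the mean. If leaving after V1 is related to the V1 score, completers' change differs from that of all patients. If the relation is the same in both groups, the distortions cancel in the interaction. If it differs, they do not. Adjusting for V0 does not remove the problem, because selection acts on V1.

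The design makes unequal selection plausible. Groups are formed by plasma level, not by randomisation (Test groups). Hypothesis 2 expects them to differ already at V1. At V1 one group receives a new regimen, while the other is told to carry on unchanged (Course of the trial, Week 4). Only the clinician who usually monitors the patient is described as unaware of group and dose. A poorly responding patient may therefore have a different reason to leave in one group than in the other. At stake is the test that decides the trial's primary claim.

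**Working it through.** The plan gives no sample size, SD, V1–V2 correlation or dropout rate, so it has no figure to reproduce. All numerical inputs below are assumptions.

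**1. Formula.** Let b be the slope of V2 on V1, and D the mean V1 of completers minus the mean V1 of all patients in a group. Ignoring covariates, the complete-pair interaction (V2−V1 in Adjusted minus V2−V1 in Standard) has

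bias = (b − 1) × (D_Adjusted − D_Standard).

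A negative value makes Adjusted look better.

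**2. Inputs, first set.** 75 per group; V1 means 11 (Standard) and 14 (Adjusted); SD 6; b = 0.6; residual SD 4.5; both groups improve by 4 points, so the true interaction is 0. Dropout is logistic in V1, with slope 0.2 to 0.25 per point where it depends on V1.

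**3. Standard error.** SD of change = √[(1 − 0.6)² × 36 + 4.5²] = √(5.76 + 20.25) = 5.1. With 25% and 15% dropout, 56.25 and 63.75 patients remain on average: 5.1 × √(1/56.25 + 1/63.75) = 0.93. Simulated values were 0.92 to 0.97, or about 0.95.

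**4. Bias.** Here b − 1 = −0.4, so a bias of 0.3 to 1.0 needs the V1 shift from dropout to differ between groups by 0.3/0.4 = 0.75 to 1.0/0.4 = 2.5 points. Results when high V1 scorers leave the Standard group:

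| Scenario | Size of complete-pair bias (HAM-D points) |
|---|---|
| Dropout 25–36% Standard, 15–20% Adjusted | 0.32, 0.43, 0.55, 0.91 |
| Dropout 20% in both, V1-dependent in Standard only | 0.49 (shift 0.49/0.4 ≈ 1.2 points) |
| Same V1 dependence and same rate in both | 0.00 |

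With dropout up to 38% and V1 dependence in the Standard group only, the bias reaches about 1.0. A likelihood analysis using all V1 and V2 data was within 0.05 of zero throughout. In these scenarios the bias makes Adjusted look better; if the Adjusted group loses the high scorers instead, the sign reverses.

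**5. Effect on the test.** By normal approximation, with z = bias/0.95, two-sided type I error is Φ(−1.96 + z) + Φ(−1.96 − z): 0.06 at a bias of 0.32, 0.09 at 0.55 and 0.16 at 0.91.

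**6. Second set of assumptions.** SD 6, corr(V1,V2) 0.5 or 0.7, V0 as covariate, V1 difference 0 or 3 points, dropout 10–30%, logit slope 1 per SD of V1, 50:50 groups (from the SAP's expected 40% below and 10% above the window):

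| Dropout pattern | Bias (points) | Type I error, total N = 100 or 200 |
|---|---|---|
| Unrelated to V1 | about 0 | 0.04–0.06 |
| Same rule in both, no V1 difference | −0.04 to 0.05 | 0.03–0.06 |
| Same rule in both, Adjusted 3 points worse at V1 | 0.04–0.18 | 0.04–0.07 |
| V1-dependent in Adjusted only | 0.16–0.89 | 0.05–0.13 |
| Opposite V1 dependence | 0.28–1.42 | 0.05–0.31 |

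Positive values make Adjusted look worse. The likelihood analysis stayed within ±0.05 points in every row; its type I error was not simulated.

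**7. Covariate terms.** With complete data and unstructured covariance, covariates entered only as main effects cancel from V2−V1, so the model returns the unadjusted interaction. In one simulated complete data set this was −0.94, against −0.73 for the covariate-adjusted change. The two agree once covariate-by-visit terms are added.

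**The case against.** **The plan does not say that only complete pairs are used.** A reader might infer this from the method's name. The text is silent, and the UKU paragraph's phrase, "using mixed model analysis of covariance (Mixed ANCOVA) where variables will be assigned as follows", also fits a likelihood mixed model. This stands: complete-pair use is one permitted reading, not a stated rule. The layout with a between-patient factor and a repeated factor, conditional on ANCOVA assumptions, still makes it a natural one. The ambiguity also leaves the choice open until the data are seen.

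**V1-related dropout alone does not bias the interaction.** A reader might infer that it does. It must shift V1 differently in the two groups. Under one common rule with Adjusted 3 points worse at V1, the bias is small: 0.04–0.18 points in the second set, and 0.14–0.25 with the first set's slopes at 15–25% dropout. This stands, and the documents have no data on dropout in either group.

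**The direction is not known.** A reader might infer that the bias favours personalised dosing. If Standard loses its high scorers, it does. But Hypothesis 2 expects Adjusted to be worse at V1, so a common rule under which high scorers leave would make Adjusted look worse.

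**The size is assumed, and moderate.** All but the most extreme of the four differential-dropout scenarios in step 4 leave type I error at about 0.06–0.09. This also stands.

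**UKU is less certain.** It was not simulated. The algebra applies to mean item scores, but items run from 0 to 3, and the alternative logistic analysis needs no pairs.

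**Conclusion.** The concern holds in a conditional form. The plan leaves open the estimation method and the treatment of patients without V2, and the classical form of the method it names would discard them. If it is run that way, and V1-related dropout acts differently by group, the primary HAM-D interaction is biased by about 0.3 to 1.0 points against a standard error of about 0.95, with 75 per group, SD 6, slope 0.6 and 15–38% dropout. With dropout acting alike in both groups the bias is near zero. None of these inputs comes from the documents, so this is a plausible risk and not a demonstrated bias. For UKU only the mechanism carries over; no size is claimed. The change should be made because it is cheap and the test affected is the primary one.

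**What to change.** In the SAP, specify the primary HAM-D analysis and the UKU item-score analysis as a likelihood-based linear mixed model with:

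- group, visit and group-by-visit;
- the covariates already listed for each outcome, and their interactions with visit;
- unstructured covariance over V1 and V2;
- every patient with V1 or V2 included.

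Report dropout between V1 and V2 by group, with V1 scores of those who left and those who stayed. The relative-change ANCOVA needs its own missing-data rule, because the mixed model does not cover it.

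**Cost.** SAP wording and slightly more analysis work; no new data. With no dropout, the model reproduces the repeated-measures ANCOVA interaction, provided covariate-by-visit terms are in both. If they are left out of the new model, the primary estimate can change even with complete data. The model relies on data being missing at random given the observed scores, group and covariates, so a sensitivity analysis for departures from that assumption is a sensible addition. Patients with neither V1 nor V2 still contribute nothing.

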(*Sample is not time dependent, it can be taken at any visit)

Week 2

Mid-Visit (Vk)

- Escitalopram plasma concentrations reach steady state.
- Plasma sample taken for the purpose of TDM and group allocation.

- Percentages of participants who are underdosed and overdosed will be measured and used to confirm previous findings [Jukić 2018]

Week 4

Visit 1 (V1)

- Participants are allocated to the “Standard dose” or “Adjusted dose” group
- Independent clinician prescribes new dosing regimen to the participants in “Adjusted dose” group, and informs patients in “Standard dose” group to continue taking the same standard escitalopram dose.
- Clinician who usually monitors given patient is unaware of the group patient is allocated to, or the dose prescribed to a patient at Visit 1.
- Outcomes measured:
 1. Clinical questionnaires
 2. Anthropometric measurements
 3. Cardiological assessment
 4. Serum samples for biochemical analyses
 5. Plasma samples to reconfirm TDM findings in VK

Week 8

Visit 2 (V2)

- Final visit of the trial and the end of the follow-up.
- Outcomes measured:
 1. Clinical questionnaires
 2. Anthropometric measurements
 3. Cardiological assessment
 4. Serum samples for biochemical analyses
 5. Plasma samples to reconfirm TDM findings in VK and V1 for Standard dosing group, and to determine whether personalized dose is optimal for the patients in Personalized dosing group.

If needed, alternative course will be used:

Week 0

Initial visit + Mid-visit (V0+k)

- Participant on the stable (longer than 2 weeks) monotherapy of Major Depressive Disorder with standard dose of escitalopram (10 mg/day) will be enrolled if other inclusion criteria are met.
- Outcomes measured:
 1. General and socio-demographic information
 2. Clinical questionnaires
 3. Anthropometric measurements
 4. Cardiological assessment
 5. Serum samples for biochemical analyses
 6. Plasma sample for the purpose of TDM and group allocation.
 7. Buffy coat samples for DNA extraction and *CYP2C19* genotyping*

(*Sample is not time dependent, it can be taken at any visit)

Week 2

Visit 1 (V1) – *Identical to the standard protocol*

- Participants are allocated to the “Standard dosing” or “Personalized dosing” group
- Independent clinician prescribes new dosing regimen to the participants in “Personalized dosing” group, and informs patients in “Standard dosing” group to continue taking the same standard escitalopram dose.

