- Clinician who usually monitors given patient is unaware of the group patient is allocated to, or the dose prescribed to a patient at Visit 1.
- Outcomes measured:
 1. Clinical questionnaires
 2. Anthropometric measurements
 3. Cardiological assessment
 4. Serum samples for biochemical analyses
 5. Plasma samples to reconfirm TDM findings in V_k

Week 6

Visit 2 (V2) – *Identical to the standard protocol*

- Final visit of the trial and the end of the follow-up.
- Outcomes measured:
 1. Clinical questionnaires
 2. Anthropometric measurements
 3. Cardiological assessment
 4. Serum samples for biochemical analyses
 5. Plasma samples to reconfirm TDM findings in V_k and V1 for Standard dosing group, and to determine whether personalized dose is optimal for the patients in Personalized dosing group.

Hypotheses:

- 1) More than one quarter of participants will be overdosed or underdosed under standard escitalopram dosing regimen (10 mg/day), as determined by TDM data 2 weeks after the beginning of the therapy.
- 2) Participants with escitalopram steady state plasma concentration outside the therapeutic window (“Adjusted dose” group) will experience reduced efficacy and more severe side effects of escitalopram therapy before dose personalization (at V1) compared to the participants with escitalopram levels within therapeutic window (“Standard dose” group) at standard dosing.
- 3) Participants with escitalopram steady state plasma concentration outside the therapeutic window (“Adjusted dose” group) will show improved efficacy and less severe side effects of escitalopram therapy after dose personalization (at V2) as compared to before (at V1), and will reach clinical outcomes comparable to the “Standard dose” group (at V2).

- 4) Decisions on whether to use personalized or standard dosing, and how to adjust personalized dose based on TDM data could have been determined before the beginning of the treatment using predictive model which, besides other predictors also includes *CYP2C19* genotyping data.

Statistical Analysis Plan

Primary outcomes:

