3. Normal metabolizer (NM): Carries *1/*1 *CYP2C19* genotype. Normal CYP2C19 enzyme activity
4. Ultra rapid metabolizer: Carries *1/*17 or *17/*17 *CYP2C19* genotype. Increased CYP2C19 enzyme activity

Multiple linear regression model will be build using selected variables:

1. Dependent variable: Plasma escitalopram concentrations at Week 2 (Vk) after the initiation of the treatment
2. Independent variables: Body mass index, PM status (0=Yes, 1=No), IM status (0=Yes, 1=No), NM status (0=Yes, 1=No), UM status (0=Yes, 1=No), Creatinine clearance, AST/ALT ratio

Other outcome measures/observations:

To further validate our primary outcome measures: escitalopram treatment efficacy and severity of adverse effects, we will use Clinical Global Impression (CGI) scales. Scores will be determined for all 3 CGI scales: for Severity of illness (CGI-S) scale at baseline, visit 1 and visit 2, and for Global improvement (CGI-I) scale and for Efficacy Index (CGI-E) at visits 1 and 2. Differences in all 3 CGI scales between visits 1 and 2 will be compared between test groups separately using ANCOVA tests with the equivalent sets of covariates to the ones used for HAM-D scale.

In all patients at baseline and at visits 1 and 2, electrocardiography will be performed in order to monitor potential QT interval prolongation. We will test for correlation between QT interval length and escitalopram plasma levels at various visits, and also we will compare changes in QT interval length between visit 1 and visit 2 in both test groups using mixed ANCOVA test adjusting for the baseline QT length.

Due to high comorbidity of anxiety and depression, and since escitalopram is frequently prescribed in anxiety disorders, we will explore severity of anxiety symptoms in all participants at baseline (V0), Week 4 (V1) and Week 8 (V2) of the treatment by using clinician reported Hamilton anxiety rating scale (HAM-A). Severity of anxiety symptoms will be compared between two test groups at two time points (V1 and V2) using mixed analysis of covariance (Mixed ANCOVA). Variables to be considered as covariates will be: Baseline HAM-A score (V0), Childhood trauma questionnaire score at V0, Age, Sex (Male=0, Female=1), Smoking status (0=Non-smoker, 1=Smoker), Alcohol consumption (0=No, 1=Yes), Metabolic syndrome (0=No, Yes).

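### HAM-D has two success rules at 0.05 with no order or direction, and the plan does not say which covariate terms enter the group-by-visit test

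*Combined protocol and SAP*

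**What the plan says.** Under Primary outcomes, the SAP analyses absolute HAM-D scores by mixed ANCOVA, with test group as fixed factor and visit (V1, V2) as repeated factor. The rule is "Positive outcome: interaction between group and visit is significant", at α = 0.05. The covariate list begins "Covariates: Baseline HAM-D score (V0), Childhood trauma questionnaire score at V0, Age, Sex (Male=0, Female=1") and goes on to smoking, alcohol and metabolic syndrome. No covariate-by-visit term is mentioned.

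The SAP then adds an ANCOVA of relative V1-to-V2 change with the same covariates. It is introduced as "another way to express the potential differences in therapy efficacy between the two test groups", but has its own rule: "Positive outcome: Test group is a significant factor", again at α = 0.05.

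The false discovery rate correction is named only for the UKU side-effect items. Hypothesis 2 expects that the Adjusted dose group "will experience reduced efficacy and more severe side effects of escitalopram therapy before dose personalization (at V1"). Hypothesis 3 expects that the same group "will show improved efficacy and less severe side effects of escitalopram therapy after dose personalization (at V2) as compared to before (at V1"). For CGI, the SAP plans a different form: "Differences in all 3 CGI scales between visits 1 and 2 will be compared between test groups separately using ANCOVA tests", with covariates equivalent to those for HAM-D.

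**The concern.** HAM-D is the primary efficacy outcome, and the SAP leaves three choices open.

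- **Which rule decides.** Two rules have equal standing, with no order and no division of α.
- **Which direction counts.** Hypothesis 3 has a direction; neither rule repeats it.
- **Which model is fitted.** The group-by-visit test is adjusted for the covariates under one reading of mixed ANCOVA and unadjusted under another.

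Two analysts could each follow the text and report different verdicts from the same data.

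**Working it through.** **Inputs.** From the documents: α = 0.05 for each rule, two visits in the repeated factor, and seven covariates with one value per patient. Roughly equal groups follow from Secondary outcomes (about 40% below plus about 10% above the window). The documents give no sample size, SD, effect size or V1 difference, so there is no planned figure to reproduce and every simulated rate below is conditional on its assumptions.

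**1. Error if either rule suffices (no effect, no V1 gap).** Two independent tests would give 1 − 0.95² = 0.0975. The two HAM-D tests are positively correlated, so the true figure is lower. Two simulations with SD about 6 gave:

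- 6.5–7.6% with 30 to 100 per group, mean V1 of 16 or 22 and a 5-point fall;
- 6.7–8.7% with 50 or 100 per group, mean V1 of 15, a 5-point fall and V1 reliability of 0.85 or 0.6.

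These are two-sided rates, so the comparison is with 5%.

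**2. Absolute and relative change when V1 differs.** Take group means of 20 (Adjusted) and 16 (Standard).

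- Equal falls of 4 points: the interaction is 4 − 4 = 0, but relative change is 4/20 = 20% against 4/16 = 25%.
- Equal relative falls of 25%: relative change is equal, but the absolute falls are 5 and 4 points, an interaction of 1 point.

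If scores fall at all, the two measures cannot both be null. Simulated with 100 to 200 patients in total, mean Standard V1 of 16 and a 5-point Standard fall:

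| Setting | Interaction rule positive | Relative-change rule positive |
|---|---|---|
| Adjusted 3 points worse at V1, equal absolute falls | 4–6% | 12–19% |
| Adjusted 4 points worse at V1, equal relative falls | 26–49% | 5% |

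**3. Direction.** If the Adjusted dose group improved 3 points less than Standard, the interaction would be significant in 89% of trials of 100 patients and over 99% of trials of 200. The literal rule would be met each time.

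**4. Covariates.** Let g be group, x a covariate with one value per patient, and u the patient effect. With x as a main effect only:

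- Y at V1 = a + γg + βx + u + e₁
- Y at V2 = a + τ + γg + δg + βx + u + e₂
- Change = τ + δg + (e₂ − e₁)

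The term βx cancels, so δ is the unadjusted group difference in change. With a covariate-by-visit term, the change becomes τ + δg + θx + (e₂ − e₁), which is ANCOVA of change.

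Random-intercept fits to two simulated data sets with both visits observed agree:

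| Covariate terms | Data set A (n = 100) | Data set B (n = 120) |
|---|---|---|
| None | −2.000 (SE 0.821) | 1.275 (SE 0.705, p = 0.07) |
| Main effects | −2.000 (SE 0.821) | 1.275 (SE 0.705) |
| Covariate-by-visit | −1.883 (SE 0.793) | 0.610 (SE 0.710, p = 0.39) |
| ANCOVA of change | −1.883 (SE 0.793) | 0.610 (SE 0.710) |

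In B, covariates were built to affect change and to differ between groups. The relative-change ANCOVA is covariate-adjusted on any reading, so under the main-effect reading the two rules also differ in adjustment.

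**The case against.** **Covariates.** The SAP lists variables, not a model equation. Classical repeated-measures ANCOVA applies the between-patient terms, covariates included, to the visit contrast, so they do adjust the interaction. The CGI plan suggests that this was the intent. This stands. A reader might infer that the covariates do nothing in the primary test; the documents do not support that, because it holds under one reading only. What remains is that the choice is not stated.

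**Two rules.** Relative change is worded as supportive, and nothing says that either rule suffices. This stands in part: the inflation is conditional and modest, and well short of 9.75%. But a supportive analysis does not normally have its own success line, and the divergence in step 2 does not depend on an either-or reading.

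**Direction.** Reading a two-sided test against a directional hypothesis is ordinary practice, and Hypothesis 3 supplies the direction. This largely stands. A reader might infer that the plan would call harm a success; that requires ignoring Hypothesis 3. One clause settles it.

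**False positives from a V1 gap.** A reader might go further and infer that the interaction rule is invalid because the Adjusted dose group starts worse. Assume a 4-point gap, V1 reliability 0.85, V0 equal between groups, and a slope of V2 on V1 severity of 0.67 without any dose effect. The interaction rule then favoured Adjusted in 33% / 57% of trials (50 / 100 per group). Relative change did so in only 4% / 5%, so the plan's second analysis would already expose the problem there. If the gap persists (slope 1), the interaction rule favoured Adjusted in 3% / 4%. Neither the gap nor the slope is in the documents. The source is allocation by plasma level with no out-of-window participant left on the standard dose, which is a limit of the design, not an error in the choice of test.

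**Conclusion.** The point holds as an under-specified primary analysis and should be fixed before analysis. The missing order and direction, the arithmetic of absolute against relative change, and the cancellation of main-effect covariates with complete V1 and V2 data all follow from the text and algebra alone. The sizes do not: the 7–9% error needs an either-rule reading with SD about 6 and 50–100 per group, and the disagreement rates need an assumed V1 gap. Confidence in the sizes is medium. The point does not show that the interaction test is biased, or that the covariates are necessarily ineffective.

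**What to change.** State under Primary outcomes:

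1. *The primary HAM-D test is ANCOVA of V1-to-V2 change on test group and the listed covariates (equivalent to mixed ANCOVA with every covariate-by-visit term).* This is the form already planned for CGI.
2. *It is positive only if significant at two-sided 0.05 in favour of the Adjusted dose group.*
3. *This is the only HAM-D success rule. Relative change is supportive and carries no success claim.*

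**Cost.** No new data are needed. Relative change loses its success claim, and with 50 per group 7 of 98 residual degrees of freedom go to covariates. For a true extra 3-point fall, no V1 gap, and covariates other than V0 HAM-D unrelated to outcome, power against the unadjusted interaction test goes from:

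- 92% to 91% (50 per group, reliability 0.85);
- 65% to 62% (50 per group, reliability 0.6);
- 91% to 90% (100 per group, reliability 0.6).

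Against an either-rule reading the 50-per-group starting points are 95% and 75%, part of which is bought with the higher error. If covariates explain 20% of change, adjustment gains power: 63% to 69% for a 2-point effect with 50 per group.

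**Limit.** The change does not remove bias from a V1 gap that the covariates do not explain. Because every out-of-window participant has the dose adjusted, report the result as an adjusted association. ANCOVA of V2 HAM-D with V1 HAM-D as a covariate may be added as an optional sensitivity analysis, with estimates and confidence intervals. It should not trigger a conclusion by disagreement in significance: with a true 3-point effect and a persisting 4-point gap, it failed to agree with 37% / 11% of true positives at reliability 0.85 (50 / 100 per group), and with 90% / 90% at 0.6.
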